Colitis (including microscopic colitis) occurred in 4 (1%) of 411 patients, including Grade 2 or 3 cases in 1 (0.2%) and 2 (0.5%) patients, respectively, receiving KEYTRUDA in Trial 1. The median time to onset of colitis was 6.5 months (range 2.3-9.8). The median duration was 2.6 months (range 0.6 weeks-3.6 months). All three patients with Grade 2 or 3 colitis were treated with high-dose corticosteroids (greater than or equal to 40 mg prednisone or equivalent per day) with a median initial dose of 70 mg/day of prednisone or equivalent; the median duration of initial treatment was 7 days (range 4-41), followed by a corticosteroid taper. One patient (0.2%) required permanent discontinuation of KEYTRUDA due to colitis. All four patients with colitis experienced complete resolution of the event. Monitor patients for signs and symptoms of colitis. Administer corticosteroids for Grade 2 or greater colitis. Withhold KEYTRUDA for moderate (Grade 2) or severe (Grade 3) colitis, and permanently discontinue KEYTRUDA for life-threatening (Grade 4) colitis.

Immune-Mediated Hepatitis

Hepatitis (including autoimmune hepatitis) occurred in 2 (0.5%) of 411 patients, including a Grade 4 case in 1 (0.2%) patient, receiving KEYTRUDA in Trial 1. The time to onset was 22 days for the case of Grade 4 hepatitis which lasted 1.1 months. The patient with Grade 4 hepatitis permanently discontinued KEYTRUDA and was treated with high-dose (greater than or equal to 40 mg prednisone or equivalent per day) systemic corticosteroids followed by a corticosteroid taper. Both patients with hepatitis experienced complete resolution of the event.

Elevated transaminases and alkaline phosphatase may be seen during treatment. Treatment should be interrupted when transaminase or alkaline phosphatase increases are accompanied by Grade 3 total bilirubin, and/or Grade 3 coagulation tests (e.g., International Normalized Ratio [INR]), or if subjects are clinically symptomatic.

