10.0 TREATMENT/ DOSE MODIFICATIONS

10.1 Unacceptable Toxicity

Causality for all adverse events should be assessed and if deemed attributable, attempts should be made toward proper attribution.

Drug-related grade 4 toxicities will require subject to discontinue all study treatment. Intolerable grade 2 and grade 3 toxicities should be managed as per dose modification guidelines listed in the table below. Pembrolizumab therapy may be continued providing the residual adverse events are within permissible ranges for pembrolizumab dosing.

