Pneumonitis	Grade 2	Withhold	Administer corticosteroids (initial dose of 1-2 mg/kg prednisone or equivalent) followed by taper	Monitor participants for signs and symptoms of pneumonitis Evaluate participants with suspected pneumonitis with radiographic imaging and initiate corticosteroid treatment Add prophylactic antibiotics for opportunistic infections
	Grade 3 or 4, or recurrent Grade 2	Permanently discontinue		
Diarrhea / Colitis	Grade 2 or 3	Withhold	Administer corticosteroids (initial dose of 1-2 mg/kg prednisone or equivalent) followed by taper	
 • Monitor participants for signs and symptoms of enterocolitis (ie, diarrhea, abdominal pain, blood or mucus in stool with or without fever) and of bowel perforation (ie, peritoneal signs and ileus). • Participants with \geq Grade 2 diarrhea suspecting colitis should consider GI consultation and performing endoscopy to rule out colitis. • Participants with diarrhea/colitis should be advised to drink liberal quantities of clear fluids. If sufficient oral fluid intake is not feasible, fluid and electrolytes should be substituted via IV

	Grade 4	Permanently discontinue		infusion.
AST / ALT elevation	3	Withhold	Administer corticosteroids (initial dose of 0.5- 1 mg/kg prednisone or equivalent) followed by taper	Monitor with liver function tests (consider weekly or more frequently until liver enzyme value returned to baseline or is stable
	4	Permanently discontinue --see exception below ²	Administer corticosteroids (initial dose of 1-2 mg/kg prednisone or equivalent) followed by taper	
Increased bilirubin	Grade 2	Withhold	Administer corticosteroids (initial dose of 0.5- 1 mg/kg prednisone or equivalent) followed by taper	Monitor with liver function tests (consider weekly or more frequently until liver enzyme value returned to baseline or is stable
	Grade 3 or 4	Permanently discontinue	Administer corticosteroids (initial dose of 1-2 mg/kg prednisone or equivalent) followed by taper	
Type 1 diabetes mellitus (T1DM) or Hyperglycemia	Newly onset T1DM or Grade 3 or 4 hyperglycemia associated with evidence of β -cell failure	Withhold	Initiate insulin replacement therapy for participants with T1DM Administer anti-hyperglycemic in participants with hyperglycemia	Monitor participants for hyperglycemia or other signs and symptoms of diabetes.

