APPENDIX I: EVENTS OF CLINICAL INTEREST & SUPPORTIVE CARE GUIDELINES FOR PEMBROLIZUMAB

Suggested supportive care measures for the management of AEs with potential immunologic etiology. Where appropriate, these guidelines include the use of oral or intravenous treatment with corticosteroids as well as additional anti-inflammatory agents if symptoms do not improve with administration of corticosteroids. These guidelines are intended to be applied when the Investigator determines the events to be related to pembrolizumab.

- **Pneumonitis:**

- For **Grade 2 events**, treat with systemic corticosteroids. When symptoms improve to Grade 1 or less, steroid taper should be started and continued over no less than 4 weeks.
- For **Grade 3-4 events**, immediately treat with intravenous steroids. Administer additional anti-inflammatory measures, as needed.
- Add prophylactic antibiotics for opportunistic infections in the case of prolonged steroid administration.

- **Diarrhea/Colitis:**

Subjects should be carefully monitored for signs and symptoms of enterocolitis (such as diarrhea, abdominal pain, blood or mucus in stool, with or without fever) and of bowel perforation (such as peritoneal signs and ileus).

- All subjects who experience diarrhea/colitis should be advised to drink liberal quantities of clear fluids. If sufficient oral fluid intake is not feasible, fluid and electrolytes should be substituted via IV infusion. For Grade 2 or higher diarrhea, consider GI consultation and endoscopy to confirm or rule out colitis.
- For **Grade 2 diarrhea/colitis** that persists greater than 3 days, administer oral corticosteroids.
- For **Grade 3 or 4 diarrhea/colitis** that persists > 1 week, treat with intravenous steroids followed by high dose oral steroids.
- When symptoms improve to Grade 1 or less, steroid taper should be started and continued over no less than 4 weeks.

- **Type 1 diabetes mellitus or T1DM (if new onset, including diabetic ketoacidosis [DKA]) or \geq Grade 3 Hyperglycemia, if associated with ketosis (ketonuria) or metabolic acidosis (DKA)**

- For **T1DM or Grade 3-4 Hyperglycemia**
 - Insulin replacement therapy is recommended for Type I diabetes mellitus and for Grade 3-4 hyperglycemia associated with metabolic acidosis or ketonuria.
 - Evaluate patients with serum glucose and a metabolic panel, urine ketones, glycosylated hemoglobin, and C-peptide.

- **Hypophysitis:**

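### Appendix I ties corticosteroids for pembrolizumab-related diarrhea/colitis to more than 3 days (Grade 2) or more than 1 week (Grade 3-4) of persistence; Table 10.2 and Section 9.1.4 state no wait, and Section 10.1 settles the conflict only in part

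*Combined protocol and SAP*

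**What the plan says.** **Appendix I, Diarrhea/Colitis.** Grade 2 diarrhea/colitis "that persists greater than 3 days, administer oral corticosteroids". Grade 3 or 4 diarrhea/colitis "that persists > 1 week, treat with intravenous steroids followed by high dose oral steroids". The appendix presents its measures as suggestions. Its opening paragraph fixes when they apply: "These guidelines are intended to be applied when the Investigator determines the events to be related to pembrolizumab".

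**Table 10.2 (Section 10.2).** The diarrhea/colitis row, against Grade 2 or 3, reads: "Administer corticosteroids (initial dose of 1-2 mg/kg prednisone or equivalent) followed by taper". No persistence condition is attached. General instruction 3 above the table puts IV corticosteroid before oral for severe and life-threatening immune-related events, again with no wait stated.

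**Section 9.1.4, Immune-Mediated Colitis.** "Administer corticosteroids for Grade 2 or greater colitis". No wait is stated. This sentence covers colitis, not diarrhea without colitis.

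**Section 10.1.** "Intolerable grade 2 and grade 3 toxicities should be managed as per dose modification guidelines listed in the table below". For Grade 4: "Drug-related grade 4 toxicities will require subject to discontinue all study treatment". Appendix I is not mentioned.

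**Cross-references.** Section 9.1.4 names Appendix I as the place for the general approach to immune-related events, and Section 10.2 also refers the reader there. No sentence says which text prevails.

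**The concern.** The same patient, with an event already judged drug-related, meets different steroid triggers depending on which part of the protocol the investigator opens. The Appendix I wait also lengthens with severity, from more than 3 days at Grade 2 to more than 1 week at Grades 3 and 4. Section 9.1.4 describes early recognition and treatment of immune-related events as critical, and the diarrhea/colitis part of Appendix I itself asks for monitoring for bowel perforation.

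What is at stake is patient safety. The conflict concerns steroid timing only. Drug handling agrees between Table 10.2 and Section 9.1.4: pembrolizumab is withheld at Grade 2-3 and permanently discontinued at Grade 4.

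**Working it through.** The plan gives no figure to reproduce here. The check is a comparison of the current provisions, followed by a rough estimate of how often the situation could arise.

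**Step 1: steroid start by grade**

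| Grade | Appendix I | Provisions with no stated wait | Settled by Section 10.1? |
|---|---|---|---|
| 2 | Oral, after more than 3 days | Table 10.2 row; Section 9.1.4 (colitis) | Intolerable events go to the table; others are not addressed |
| 3 | IV, after more than 1 week | Table 10.2 row; general instruction 3; Section 9.1.4 (colitis) | Sent to the table, but without reference to Appendix I |
| 4 | IV, after more than 1 week | General instruction 3; Section 9.1.4 (colitis) | No; only drug discontinuation is addressed |

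The Grade 4 steroid cell of the diarrhea/colitis row is blank in the text available. It may be a merged cell, so nothing is inferred from it.

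**Step 2: is the wait consistent with the rest of Appendix I?** It is not. For Grade 3-4 pneumonitis the appendix calls for IV steroids at once. Its steroid instructions for hypophysitis, hyperthyroidism, hepatic and renal events carry no persistence condition. Diarrhea/colitis is the exception.

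**Step 3: could the wait be time for diagnostic work-up?** That would explain a pause before attribution. Appendix I applies once the event has been attributed to pembrolizumab, and work-up would not explain a longer wait at higher grades.

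**Step 4: how often could it arise?** The inputs are the melanoma counts in Section 9.1.4, where colitis "occurred in 4 (1%) of 411 patients, including Grade 2 or 3 cases in 1 (0.2%) and 2 (0.5%) patients, respectively", and n = 28 (evaluable target) to 35 (enrolment ceiling, Section 16.4). The assumption is that these rates carry over to hepatocellular carcinoma. The formula is P(at least one) = 1 − (1 − p)^n, with expected number n × p.

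| Event | p | Expected, n = 28 | Expected, n = 35 | P(at least one), n = 28 | P(at least one), n = 35 |
|---|---|---|---|---|---|
| Grade 2-3 colitis | 3/411 = 0.730% | 0.20 | 0.26 | 18.5% | 22.6% |
| Grade 3 colitis | 2/411 = 0.487% | 0.14 | 0.17 | 12.8% | 15.7% |

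The exact 95% limits on 3/411 are 0.15% and 2.12%. With these, the chance of at least one Grade 2-3 colitis runs from 4.1% (lower limit, n = 28) to 52.7% (upper limit, n = 35).

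These are chances that the event occurs, not that steroids are delayed. They leave out diarrhea without colitis, and the counts contribute no Grade 4 case.

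**The case against.** The best case for the plan has five parts.

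- **Appendix I only suggests.** It does not forbid earlier steroids, and Section 8.4 leaves supportive care to the treating investigator. This is true and limits the strength of the conflict. But two sections send the reader to Appendix I, and the only timing it offers for diarrhea/colitis is the delayed one.
- **Section 10.1 already sends Grade 3 to the table.** This has real force: on a plain reading the table wins for Grade 3 and for intolerable Grade 2. Other Grade 2 events and Grade 4 steroid timing remain open, and a reader who goes straight to Appendix I is not told that it yields.
- **Silence on timing is not an order to start at once, and general instruction 3 may set only the order of routes.** Both readings are possible. If general instruction 3 is set aside, the Grade 4 contrast rests on Section 9.1.4 and so on colitis alone. But reading the silent provisions together with Appendix I would only confirm a wait of more than a week at Grades 3 and 4, against the stress Section 9.1.4 lays on early treatment.
- **A separate guidance document may settle the timing.** Section 9.1.4 refers sites to one. It is not part of these documents, so its effect is unknown, and the protocol should be consistent on its own terms.
- **The probabilities do not measure harm, and 35 is an enrolment ceiling.** Agreed. They show only that the situation is plausible in a trial of this size, and the number treated may be below 35.

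**Conclusion.** The concern holds: the text is wrong as written and should be corrected. Current provisions differ on when to start steroids for drug-related diarrhea/colitis by more than 3 days at Grade 2 and more than 1 week at Grades 3 and 4, and no rule of precedence fully resolves the difference. The gap is clearest for Grade 4 colitis and for Grade 2 events that are not intolerable. For Grade 3, Section 10.1 favours the table but leaves the contrary text in Appendix I standing. For diarrhea without colitis, the contrast rests on Table 10.2 alone.

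The textual finding needs no numerical assumption. The 18.5% to 22.6% and 12.8% to 15.7% figures rest on melanoma rates applying to this population and on 28 to 35 patients being treated. There is no effect on the sample size, the error rates or the DCR analysis.

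**What to change.** 1. In the diarrhea/colitis bullets of Appendix I, delete the two persistence conditions (more than 3 days for Grade 2, more than 1 week for Grade 3 or 4). Steroids then start at Grade 2 or greater, with IV first for Grade 3-4.
2. Add one sentence to Section 10.2: where Table 10.2 and Appendix I differ on the management of diarrhea/colitis, Table 10.2 governs.

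The cost is two deletions and one added sentence in a protocol amendment. No procedures, visits or patients are added.
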